Nevertheless, the literature on TMS for OCD remains noisy and the clinical outcomes, while promising, need improvement. An important source for this variability is the lack of individualized methods to identify and target the appropriate cortical nodes for stimulation. Our study will address this by using individual fMRI maps to identify the target and neuronavigation technology to precisely and consistently inhibit it with TMS. Another critical variable driving these inconsistencies in the field is the lack of mechanistic understanding of the effects of TMS in OCD. A priori hypotheses about disease mechanisms have driven the choices of targets of stimulations in the published clinical trials (based on a fairly robust understanding of the circuitry involved in the pathophysiology of OCD), but most studies limited themselves to measuring clinical outcomes. While this pragmatic approach is valuable, it leaves too many open questions and requires too many assumptions. Our study will innovate by proposing a translational systems neuroscience approach to understanding not only the safety and efficacy of TMS in patients with OCD, but also the physiological and anatomical changes driving (or resisting) response and remission.

II. Specific Aims

In this proposal we will apply functional neuroimaging-guided inhibitory rTMS to the pre-SMA in patients with OCD, integrating neuroimaging, behavioral and clinical research tools in a randomized controlled clinical trial. We will assess the safety and efficacy of this novel individualized strategy, study the mechanism of action at the circuit-level, and identify biomarkers and predictors of response.

Aim 1: To assess the efficacy of fMRI-guided 1HZ rTMS over the pre-SMA:

We hypothesize that patients randomized to 6 weeks of daily 1Hz rTMS will have a greater reduction in OCD symptom severity than patients randomized to identical placebo stimulation.

Aim 2: To identify the mechanisms of action of TMS at the circuit-level:

Hypothesis 2.1: We hypothesize that decreased connectivity between the pre-SMA, the Orbito-Frontal Cortex (OFC) and dorsal Anterior Cingulate Cortex (dACC) will correlate with clinical improvement.

Hypothesis 2.2: We hypothesize that TMS would improve fear extinction retention from pre- to post-treatment, and increase functional activation of the fear extinction network during extinction recall. The extinction network includes the ventromedial prefrontal cortex (vmPFC), dACC, and hippocampus.

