Aim 3: To identify biomarkers and predictors of treatment response:

Hypothesis 3.1: We hypothesize that pathological hyperconnectivity between the pre-SMA, the Orbito-Frontal Cortex (OFC) and dorsal Anterior Cingulate Cortex (dACC) will correlate with OCD symptom severity in the pre-TMS scans.

Hypothesis 3.2: We hypothesize that (a) pathological hyperconnectivity between the pre-SMA the Orbito-Frontal Cortex (OFC) and dorsal Anterior Cingulate Cortex (dACC) and (b) early reduction of this pattern after week 1 of TMS will predict positive clinical outcomes after TMS.

III. SUBJECT SELECTION

There will be two different groups of patients with OCD in this study: one will receive active stimulation and one sham stimulation (i.e. placebo). We will recruit as many patients as are needed in order to obtain 20 completers per group (i.e. 40 patients in total). We expect an early termination rate of 30%, and we will anticipate the need to recruit and consent a total of 58 patients overall.

Inclusion Criteria:

- 1) 18-65 years of age.
- 2) Proficient in English.
- 3) A diagnosis of primary OCD (as determined by SCID).
- 4) Yale-Brown Obsessive Compulsive Scale total score ≥ 16 .
- 5) Normal (or corrected) vision.
- 6) Stable OCD medication regimen or OCD medication free for \geq 12 weeks prior to study.

7) Able to give informed consent.

Exclusion Criteria:

- 1) Current or history of neurologic or psychiatric disease (e.g., mental retardation, dementia, brain damage, or other cognitive impairment) that would interfere with ability to engage in TMS
- 2) Psychopathology not appropriate for the treatment (e.g., manic episode or psychosis)
- 3) Substance abuse or dependence that is current or within the last six months or use of an illicit drug that is not prescribed, as indicated by a urine drug screen and/or clinical inference.
- 4) Use of anticonvulsants within 2 weeks prior to study (to be ruled out by a urine drug screen.
- 5) Use of Tricyclic Antidepressants (e.g. Clomipramine).
- 6) Use of psychotropic medication is allowed (except for the limitations specified on use of OCD regimens, anticonvulsants, and tricyclic antidepressants).
- 7) Documented resistance to 4 or more valid pharmacological trials of 2 or more different medication classes (e.g. SSRIs and TCAs).
- 8) Previous exposure to TMS.
- 9) Major/chronic medical conditions.
- 10) History of head injury resulting in prolonged loss of consciousness and/or neurological sequelae.

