2.1 Phase 1: Randomized placebo controlled

Patients will be randomized to receive real or sham rTMS using the variable-sized permuted blocks randomization algorithm (with a maximum block size of 4), with randomization stratified by symptom severity (Y-BOCS total score ≤31 vs. >31) and age $(\le 34 \text{ vs.} > 34 \text{ years at entry})$, to ensure balance in these factors across arms in this small study. Randomizations will be conducted in SAS using procedures outlined by Efird (2011) [Efird, J. Blocked Randomization with Randomly Selected Block Sizes. Int. J. Environ. Res. Public Health., 8, 15-20]. The randomization codes generated by our statistician/data manager for each of the 4 strata will be communicated to the study coordinator at the time of randomization (i.e. at the patient's baseline visit), based on the stratum to which the patient belongs. Patients will be blinded to their treatment arm. Patients will receive 6 weeks of daily treatments Monday through Friday (not on weekends). There will be 3 MRI sessions that will take place (i) within 2 weeks prior to the first TMS session, (ii) at the end of week 1 of treatment and (iii) within 2 weeks after the last TMS session. Longitudinal clinical assessments will take place throughout the course of study at the end weeks 2, 4 and 6 of TMS, in addition to a last assessment 3 months after TMS. Physiological assessments to measure cortical excitability and

plasticity in the motor cortex using single and paired-pulse TMS will also take place the 1st day of treatment and at the end of weeks 2, 4 and 6 of TMS.

Baseline TMS Neurophys TMS Neurophys. TMS Neurophys TMS Neurophys. 8 & 8 8 Clinical Clinical Clinical Clinical Clinical Assessment Assessment Assessment Assessment Assessment 3 mo MRI MRI MRI TMS (6 weeks) Post-TMS

Figure 1: Clinical Trial Design for Phase 1

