Subjects will view two rooms presented on a monitor, both of which differ in color and content (e.g., an office and a kitchen). The conditioned stimuli (CSs) will be different cues in the room. The CS+ and the US will only be presented in one context (conditioning context; CX+). The other context will be used for extinction training (CX-). Neither CS+ presented in the context of the CX-, nor a CS- presented in either context, will ever be paired with the US. In one of the four possible CS-CX combinations, for example, the office will serve as the dangerous context, in which the subjects will receive electric currents only when the yellow light is on, whereas the kitchen will serve as the safe context, in which no electric currents will be delivered. On day 2, subjects are placed back in the magnet and will be presented with additional extinction trials to CSs in pseudorandomorder.

As of February 27th, 2018, the fear conditioning paradigm will no longer be administered to participants in this study. All fear conditioning data collected prior to February 27th will be analyzed.

VI. BIOSTATISTICAL ANALYSIS

Analysis of Aim 1: To compare change in OCD symptom severity by treatment group, we will utilize a mixed effects linear regression model with Y-BOCS total score as the outcome, a random effect for time (study week), a fixed effect for group (rTMS versus placebo stimulation), and the interaction between time and treatment group (which is the covariate of interest). We will also control for potential confounding by any covariates that are significantly imbalanced between the treatment groups.

Analysis of Aim 2.1: Specification of the analyses examining whether decreased connectivity between the pre-SMA, the Orbito-Frontal Cortex (OFC) and dorsal Anterior Cingulate Cortex (dACC) correlates with clinical improvement can be found below, in the MRI data section - Resting state Connectivity Analysis.

Analysis of Aim 2.2: Specification of the analyses examining whether TMS improves fear extinction retention from pre- to post-treatment, and whether increased functional activation of the fear extinction network (vmPFC, dACC, and hippocampus) during extinction recall can be found below, in the MRI data section - Fear Extinction.

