Analysis of Aim 3: To identify biomarkers and predictors of treatment response, we will us linear regression analysis to examine predictors of clinical improvement. The outcome will be the post-treatment Y-BOCS score, the covariate of interest will be each ROI (examined in separate models to begin with, to avoid issues of collinearity), and we will control for the pre-treatment Y-BOCS score. Univariately significant predictors will then be entered into a multivariate linear regression model using step-wise selection (alpha=0.10 to enter, alpha=0.05 to stay).

TMS neurophysiology

Numeric values for each of our 5 physiological measures will be obtained at each of the established times (baseline, week 2, week 4, week 6). A general linear model will be used to assess the difference in longitudinal progression of these measures between the active and placebo group.

MRI data

Fear Extinction

During the extinction training on day 1, the principal contrast for the fMRI data will be CS+ vs. CS-, to establish the substrates of extinction learning. During extinction recall on day 2, the principal contrast will be CS+1 vs. CS+2. Analyses of SCR will test for group x condition interactions for OCD vs. HC with respect to CS2 vs. CS1. With respect to the fMRI data, the initial analysis will involve assessing for a main effect of condition (across both groups), by comparing CS1 vs. CS2 during extinction learning and recall. Finally, voxel-wise analyses will also be performed to identify specific loci of significant group x condition interactions (OCD, HC x CS2, CS1) within designated prefrontal search territories of interest.

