Two-tensor whole brain tractography will be implemented for tract analysis. This form of tractography involves a recursive process that both fits local parameters at each step and propagates the fiber in the most stable direction, allowing simultaneous tractography and model estimation. This model also uses a covariance matrix to measure confidence, which reduces false positives, and implements two eigenvalues per voxel, which improves resolution of and accounts for branching and crossing fibers. Whole-brain tractography will be used to best account for all potential tracts among the ROIs, which may be otherwise limited in solely ROI-based tractography (Yang et al., 2014).

Power for the Primary Aim

For the primary analysis comparing change in Y-BOCS total score by treatment group, with 20 patients per group and a two-sided alpha of 0.05, we will have 90% power to detect an effect size of 1.06. Due to the novelty of our approach, no comparable data exist to inform the power calculation. However, Mantovani et al. (2010) examined change in Y-BOCS total score among 18 OCD patients (completers) randomized to 4 weeks of similar rTMS or sham treatment. Based on their reported F-statistic comparing change in Y-BOCS total score after 4 weeks of treatment, their observed effect size,

expressed as Cohen's d (Thalheimer & Cook, 2002), was 1.8. Based on these results, we believe that our study will be adequately powered to detect anticipated effect sizes.

VII. RISKS AND DISCOMFORTS

Participation in this study poses minimal foreseeable risks. Patients may experience psychological discomfort when discussing psychiatric history and/or current psychiatric symptoms or side effects. Answering detailed questionnaires may also create some inconvenience for subjects. Confidentiality of all subjects will be protected per institutional and federal requirements.

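### The Aim 3 model omits randomised arm and states no analysis set, so if the arms are pooled, week-1 connectivity change (Hypothesis 3.2(b)) is confounded with treatment

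*Combined protocol and SAP*

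**What the plan says.** Section VI, Analysis of Aim 3, opens: "To identify biomarkers and predictors of treatment response, we will us linear regression analysis to examine predictors of clinical improvement". The model follows: "The outcome will be the post-treatment Y-BOCS score, the covariate of interest will be each ROI", one ROI per model at first, with pre-treatment Y-BOCS as the only adjustment. ROIs that are significant singly then go into a stepwise regression. Arm appears in neither step. The section does not say whether the models use both arms, the active arm only, completers, or scores from the open-label phase 2.

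Nothing elsewhere fills the gap. The resting-state connectivity section plans an ANCOVA without naming arm. The 20 completers per group in section III are a recruitment target. Where the plan means to use arm, it says so: Aim 1 has "a fixed effect for group (rTMS versus placebo stimulation), and the interaction between time and treatment group", and the TMS neurophysiology analysis will "assess the difference in longitudinal progression of these measures between the active and placebo group".

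Hypothesis 3.2 in section II has two predictors: (a) hyperconnectivity before treatment, and (b) that "early reduction of this pattern after week 1 of TMS will predict positive clinical outcomes after TMS". Section V.2.1 places the second and third scans "ii) at the end of week 1 of treatment and (iii) within 2 weeks after the last TMS session", so predictor (b) is measured after randomisation.

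**The concern.** Two issues follow from the missing arm term, and they differ in kind.

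For week-1 change the issue is confounding. The trial expects active TMS to lower Y-BOCS (Aim 1) and links falling connectivity to improvement (Hypothesis 2.1). If active TMS also lowers connectivity by week 1, then in a pooled model without arm a patient's week-1 change partly tells us which arm the patient was in. It could pass as a biomarker while carrying no information on who does well within either arm.

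For baseline ROIs the issue is what may be claimed. Section II sets out to "study the mechanism of action at the circuit-level, and identify biomarkers and predictors of response" within a randomised sham-controlled trial, and the Aim 3 text moves from treatment response to clinical improvement, which sham patients can also show. An ROI that predicts improvement equally well under sham could be reported as a predictor of response to TMS.

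**Working it through.** **1. The plan's own figure.** The only power statement is for Aim 1: "with 20 patients per group and a two-sided alpha of 0.05, we will have 90% power to detect an effect size of 1.06". Noncentrality is 1.06 × √(20/2) = 3.35 on 38 df, giving 90.4% power (91.8% by normal approximation), so it reproduces. Recruitment does too: 40/(1 − 0.30) = 57.1, rounded up to 58. No power or connectivity effect size is given for Aim 3, so every effect below is an assumption.

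**2. Set-up.** There are 20 patients per arm. Post-treatment Y-BOCS = 0.5 × baseline − d × arm + slope × ROI + noise. The ROI has SD 1 within arm, residual SD is 0.87 (= √(1 − 0.5²)) or 1.0, and tests are two-sided at 0.05. Here d is the treatment effect on Y-BOCS and s the shift that active TMS causes in week-1 connectivity. The value 1.06 is borrowed from the Aim 1 power statement as an upper scenario; it is not an expected connectivity shift.

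**3. Week-1 change with no within-arm link (slope 0), arms pooled, arm omitted.** With equal arms, the variance of the arm indicator is 1/4. The spurious slope has size (d × s/4)/(1 + s²/4).
- d = s = 1.06: 0.2809/1.2809 = 0.219. At residual SD 1.0 the remaining variance is 1 + 0.2809 − 0.219² × 1.2809 = 1.219. Noncentrality is 0.219 × √(40 × 1.2809/1.219) = 1.42, so about 28% of trials are significant (t, 37 df). At residual SD 0.87 the same steps give 1.59 and about 34%.
- d = s = 0.5: 0.0625/1.0625 = 0.059, giving about 6.5–7%.

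Simulation (20,000 trials per cell) agrees. Ranges run from residual SD 1.0 to 0.87:

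| Y-BOCS effect d | s = 0.3 | s = 0.5 | s = 0.8 | s = 1.06 |
|---|---|---|---|---|
| 0.5 | 5.5–5.6% | 6.2–6.9% | 8.2–9.8% | 11.1–12.9% |
| 0.8 | 6.3–6.4% | 8.2–9.2% | 13.2–15.9% | 18.7–22.7% |
| 1.06 | 6.9–7.7% | 10.4–12.3% | 19.0–22.3% | 27.8–33.6% |

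A separate rerun gave 27–33% for the last cell. With d = 0 the rate is 5%. With arm in the model it is 4.7–5.3%, and in active patients only 4.8–5.2%.

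**4. Baseline ROI.** Randomisation makes it independent of arm, so a truly null baseline ROI is flagged 5% of the time in every model. A purely prognostic ROI (slope 0.5 in both arms, d = 0.5 to 1.06) is flagged in 74–89% of pooled fits and 51–62% of active-only fits, against 5% for ROI x arm. An ROI that works only under active TMS (slope 0.5) is flagged in 50–61% of active-only fits, about as often as the prognostic one. The active-only fit therefore cannot tell the two apart, and the pooled fit estimates a single common slope.

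**5. Is ROI x arm the right criterion for week-1 change?** Take a full mediator: TMS shifts the ROI by 1.06 SD, the slope is 0.5 in both arms, and there is no direct arm effect. ROI x arm is significant in only about 5% of trials. The ROI term with arm in the model is significant in 82–90%. The interaction would miss the very pathway the trial proposes.

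**6. Interaction power for a baseline ROI that predicts only under active TMS.** At residual SD 1.0 to 0.87 it is 30–38% for a slope of 0.5 SD and 62–74% for 0.8 SD. The median half-width of the 95% interval is 0.69 to 0.59 SD.

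**The case against.** The strongest reply is that the plan never promises a comparison with sham in Aim 3. Hypothesis 3.2 speaks of outcomes after TMS, and the analysis text of predictors of improvement. If the aim is outcome among TMS-treated patients, an active-only fit answers it, and it has more power than the interaction. This stands. A reader might infer that the model cannot serve Aim 3 at all; the documents do not support that, because they do not say which claim is meant.

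A reader might also take the 74–89% for a prognostic baseline ROI as a false-positive rate. It is power to detect a real association, and misleads only if the result is then called specific to TMS, which the plan does not say it will do.

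Thirdly, the confounding needs two things the plan leaves unstated: that arms are pooled, and that week-1 change enters as the ROI. The second is inferred from Hypothesis 3.2(b). The high rates also need large assumed effects; when both are 0.5 SD the excess over 5% is small. All of this is correct and limits the size of the point. It does not remove it: on the plan's wording both conditions are natural, and adding arm corrects the error rate at every effect size examined.

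Finally, one might want a significant ROI x arm term before any ROI is called a predictor of TMS response. Step 5 shows why that rule is unsound for week-1 change.

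**Conclusion.** The point holds in conditional form. The omission of arm and of an analysis set is plain in the text. If the model is fitted to both arms with week-1 change as predictor, its false-positive rate rises from 5% to about 6–13% at a Y-BOCS effect of 0.5 SD, and to 27–34% only when effect and shift are both 1.06 SD. These figures rest on assumed effects, 20 per arm and a linear model.

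For baseline ROIs there is no inflation under the null. The limit is on interpretation: neither fit can support a claim of prediction for TMS as opposed to sham. It would be wrong to infer that the whole of Aim 3 fails or that the efficacy result is in doubt. Hypothesis 3.1 uses pre-treatment scans and severity, and Aim 1 has its own model with arm; both are unaffected. This should be corrected before analysis, as a matter for a secondary aim.

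**What to change.** For Hypothesis 3.2:
- State the analysis set (both arms or active only; completers or all randomised; whether phase 2 scores are used) and the intended claim.
- Include randomised arm in every model that pools the arms, the stepwise model included.
- For baseline ROIs (3.2(a)), also fit ROI x arm. Report the interaction estimate and the within-arm slopes with 95% confidence intervals. Describe a baseline ROI as specific to TMS only on the interaction; otherwise call it a predictor of outcome.
- For week-1 change (3.2(b)), report the arm-adjusted slope and the within-arm slopes with 95% confidence intervals. Do not make the interaction the criterion.

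Cost: a change of wording and one or two degrees of freedom; the sham scans and scores are already planned. Adding arm also helps: in a rerun, power for a prognostic baseline ROI rose from 75–82% to 82–90%. The real price is the low interaction power shown in step 6: few baseline ROIs will be shown to be TMS-specific, and most true interactions of 0.5 SD will not be distinguished from zero.

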With respect to SCR analyses, the SCR for each CS will be calculated by subtracting the mean level for the 2 s immediately preceding CS onset from the highest value among those recorded during the 10-s CS interval. Values will be subjected to repeated measures ANOVA to test hypotheses regarding both within-group and between-group differences at an alpha of p<0.05. Significant interactions will be followed-up with t-tests where indicated. Change in clinical symptoms from pre- to post-treatment, such as the change in YBOCS scores will be correlated with improved extinction retention index from pre- to post-treatment. Voxel-wise regression using change in YBOCS scores will be conducted against BOLD responses during extinction learning and recall to identify changes in functional activation of brain regions associated with change in clinical symptoms.

Multi-Source Interference Task

Standard task-based neuroimaging analyses procedures will be used to analyze the brain activity resulting from patients performing the MSIT in the scanner, including preprocessing and statistical parametric mapping using general linear models.

Resting state Connectivity Analysis

Functional connectivity analysis will employ a regional approach based on Biswal (Biswal, Yetkin, Haughton, & Hyde, 1995) and extended in Fox (Fox et al., 2005) and Vincent (Vincent et al., 2006). This approach has been previously used by our group and

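### The only group contrasts named for Hypothesis 2.2 compare OCD patients with HC, a group the trial does not enrol; no active-versus-sham by time test of fear extinction is stated

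*Combined protocol and SAP*

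**What the plan says.** Section II, Hypothesis 2.2, is a statement about treatment: "TMS would improve fear extinction retention from pre- to post-treatment", with greater activation of the extinction network at recall. It then lists the regions: "The extinction network includes the ventromedial prefrontal cortex (vmPFC), dACC, and hippocampus".

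Section VI (Analysis of Aim 2.2) gives no model of its own and refers the reader to the Fear Extinction subsection under MRI data. That subsection names two group contrasts:

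- SCR: "Analyses of SCR will test for group x condition interactions for OCD vs. HC with respect to CS2 vs. CS1".
- Voxel-wise fMRI: a search for "specific loci of significant group x condition interactions (OCD, HC x CS2, CS1) within designated prefrontal search territories of interest".

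It also plans a main effect of condition over both groups and, for SCR values, a "repeated measures ANOVA to test hypotheses regarding both within-group and between-group differences at an alpha of p<0.05". Change in Y-BOCS "will be correlated with improved extinction retention index from pre- to post-treatment", and a voxel-wise regression relates Y-BOCS change to BOLD response.

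Section III describes who is enrolled: "There will be two different groups of patients with OCD in this study: one will receive active stimulation and one sham stimulation". A primary OCD diagnosis is an inclusion criterion. Section V.5.2 limits the fear paradigm to patients randomized before 27 February 2018 and says that all data collected before that date will be analysed.

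**The concern.** The two group contrasts compare a diagnosis, and one of the two diagnostic groups is absent from the trial. They cannot be run on trial data. With a control group added they would still estimate how OCD patients differ from controls, not what TMS does, because they contain neither treatment arm nor visit.

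Once they fall away, the subsection has no stated test of whether real rather than sham stimulation changed extinction. The analyst would have to choose the outcome, the factors and the regions with the fear data already in hand. The analyses that remain runnable do not fill the gap. In particular, retention change can follow Y-BOCS change within each arm even when TMS has no effect on retention, so a significant correlation could be read as support for Hypothesis 2.2 when it is not.

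**Working it through.** **1. Hypothesis against planned analyses.** Hypothesis 2.2 needs a comparison of active with sham, in change from pre to post, on (a) the retention index and (b) recall activation.

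| Planned analysis (Section VI, Fear Extinction) | Groups named | Pre/post factor | Runnable | Tests Hypothesis 2.2 |
|---|---|---|---|---|
| SCR group x condition | OCD, HC | no | no | no |
| Voxel-wise fMRI group x condition | OCD, HC | no | no | no |
| fMRI main effect of condition | pooled | no | yes, in patients | no |
| SCR repeated measures ANOVA | not named | not named | only once factors are chosen | not as written |
| Y-BOCS change with retention change | none | yes | yes | no arm term |
| Voxel-wise regression on Y-BOCS change | none | Y-BOCS change only | yes | no arm term |

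Two of the two named group contrasts have 0 subjects in the HC cell. HC is never spelled out. Healthy controls is the natural reading, and any group without OCD is ineligible under Section III.

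**2. Comparison with the rest of Section VI.** Aim 1 specifies a time by treatment group interaction. TMS neurophysiology plans to "assess the difference in longitudinal progression of these measures between the active and placebo group". The omission is therefore particular to Hypothesis 2.2.

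**3. Regions and labels.** The voxel-wise group search is confined to prefrontal territory, but the hypothesis includes the hippocampus. The labels CS+1/CS+2 and CS1/CS2 are not tied to the stimuli in Section V.5.2, which describes only a CS+ and a CS-.

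**4. What a between-arm test could detect.** With two visits, arm x time is a two-sample t test on change, with 2n-2 degrees of freedom and noncentrality d·√(n/2), at two-sided alpha 0.05. As a check on the method, the protocol states 90% power for d = 1.06 with 20 per group (Aim 1). The noncentral t gives 90.4% power at 1.06, and 90% power at d = 1.05, so the two agree. The documents do not give the number per arm with pre and post fear data; the values of n below are assumptions.

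| n per arm (assumed) | d at 80% power | d at 90% power |
|---|---|---|
| 5 | 2.02 | 2.35 |
| 10 | 1.32 | 1.53 |
| 15 | 1.06 | 1.23 |
| 20 | 0.91 | 1.05 |

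**5. Why the correlation cannot stand in.** Assume no arm effect on retention change X, an arm effect of 1.06 SD on Y-BOCS improvement Y, and a within-arm correlation r. Then Y = z1 + 1.06·arm and X = r·z1 + √(1-r²)·z2. Share of 20,000 simulated trials with p < 0.05:

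| n per arm | r = 0.3 | r = 0.5 | r = 0.6 | Arm test on X |
|---|---|---|---|---|
| 10 | 20% | 50% | 70% | about 5% |
| 20 | 38% | 83% | 95% | about 5% |

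Hand check for r = 0.5: the variance of Y over all patients is 1 + 1.06²/4 = 1.281, so the correlation over all patients is 0.5/√1.281 = 0.442, and its Fisher z is 0.475. With 20 patients, 0.475·√17 = 1.96, which is about 50% power. With 40 patients, 0.475·√37 = 2.89, which is about 82%. Both agree with the simulation.

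The 50% and 83% are power to detect a real within-arm association, not error rates. They show only that a significant correlation is compatible with no effect of TMS on retention.

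**The case against.** The best defence is that HC is a mislabel and the intent is recoverable. Section III defines the trial's two groups as active and sham, the TMS neurophysiology text just before the MRI section names the active and placebo groups, and the ANOVA sentence covers within-group and between-group differences. Read together, these could mean active vs. sham for SCR. As a guess at intent this is fair. As a specification it fails: the sentence names neither arm nor visit, and the only groups named in that subsection are OCD and HC. It also covers SCR only, so recall activation, the second half of the hypothesis, has no between-arm test on any reading.

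Other objections stand in part:

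- The simulation assumes a true association and then detects it. With no arm effect on Y-BOCS the rates rise to 64% and 92%; with r = 0 they stay near 5%. The logical point needs no simulation, and the plan does not itself offer the correlation as a test of treatment.
- The detectable effects describe small samples, not this defect, and apply equally to the proposed test.
- The prefrontal limit applies only to the voxel-wise group interaction. The condition main effect and the regression carry no such limit, so the hippocampus is not excluded from the plan altogether.
- Fear data collection stopped in February 2018 and this protocol is dated August 2020. A test added now is also chosen after collection. The rewrite cannot undo that; it can only make the choice explicit.

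**Conclusion.** The point holds and should be fixed. Both named group contrasts for Hypothesis 2.2 depend on a group that the trial does not enrol, and no active-versus-sham by time test of extinction retention or recall activation is stated. This follows from the text alone. The assumed numbers per arm and within-arm correlations serve only to show scale.

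The reach is limited. One mechanistic hypothesis is affected, in an unstated subset of patients, on a paradigm that has been discontinued. The Aim 1 analysis and its power statement are untouched, and the condition contrasts, the correlation and the voxel-wise regression can still be run in patients. The analysis is nonetheless live, because the plan commits to analysing all fear data already collected.

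**What to change.** Rewrite the Fear Extinction paragraph of Section VI as follows:

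- Replace OCD vs. HC with active vs. sham in the SCR and voxel-wise analyses.
- Test arm x time (pre, post) on the extinction retention index and on recall activation in vmPFC, dACC and hippocampus, and name arm and visit as the factors of the repeated measures ANOVA.
- Define CS+1/CS+2 and CS1/CS2 by the stimuli shown.
- Report the number per arm with both pre and post fear data, and give the arm difference with its confidence interval.
- Label the result exploratory, for two reasons: only patients randomized before 27 February 2018 contribute, and the test is being specified after those data were collected.
- Keep the Y-BOCS correlation as a supporting analysis, with arm as a covariate.

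The cost is one rewritten analysis paragraph and one count per arm. No new data are needed.
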